### Statistical Analysis Plan

This study involved a single-group, pre-post design. Paired t-tests were used to determine the effect of the *PreCharge* intervention on the primary and secondary outcomes. The primary outcome was change, from pretest (baseline) to posttest (30 day follow-up), in resilience as measured by the Connor Davidson Resilience Scale (CDRISC-10). Secondary outcome measures include change in psychological flexibility (as measured by the Acceptance and Action Questionnaire – version 2 (AAQII). between pretest (baseline) and posttest (30 day follow-up) assessments. Cohen's d was used to assess the magnitude of the differences.

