Previvors Recharge: A Resilience Program for Cancer Previvors (PreCharge)

NCT06378749

Unique Protocol ID: R43CA275673

March 21, 2023

Unique Protocol

Objective:

The purpose of this research was to assess in a 30-day pilot test the acceptability and feasibility of PreCharge, a digital program delivered via text messaging and online activities designed to increase resilience and adaptive coping among previvors—individuals with Hereditary Cancer Syndromes (HCS) who have not been diagnosed with cancer. PreCharge is tailored to users' levels of resilience and adaptive coping and addresses previvor-specific needs related to: 1) information; 2) healthcare navigation; 3) processing difficult emotions; 4) social support; and 5) self-care.

Design:

As this was a Phase I study, it entailed a single-group, pre-post pilot of the PreCharge program.

The PreCharge program has various components including:

- **Immediate.and.Ongoing.Tailored.Communications;** Following the baseline assessment, participants received onscreen feedback tailored to their responses. This feedback highlighted the importance of resilience and adaptive coping for previvors and described how the program aimed to enhance those skills. Participants' responses also guided daily text communications. Daily text messages provided tailored guidance—matched to each user's responses—about resilience and coping strategies. Periodic reassessments conducted via SMS ensured that communications remained relevant to participants' evolving needs.
- **Online.Portal.** Upon completion of the baseline assessment, participants gained access to a portal homepage which featured interactive activities and tools designed to address their resilience and coping. The portal included links to additional resources, an account page, and a log-out button. For research purposes, study information was also accessible from this page during the pilot.
- **Just-in_Time.Assistance.** In addition to daily text messages, participants could access “just-in-time assistance” by indicating upcoming medical appointments or texting trigger words. Appointment-related communications were sent via SMS three days before, on the day of, and three days after an appointment to address “scanxiety” and other concerns in a timely manner. Participants could also text trigger words at any time to receive immediate support. In response to trigger words,

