PreCharge provided participants with timely guidance for improving moods, practicing gratitude, and managing stress.

Methods:

Recruitment for the 30-day pilot test began in April 2024. Participants were recruited with the help of two leading previvor advocacy organizations: Facing Our Risk of Cancer Empowered (FORCE) and AliveandKick'n. From recruitment materials distributed by our recruitment partners, prospective participants were directed to a study landing page which began with a brief overview of the study, followed by "Frequently Asked Questions," that addressed several elements of informed consent. The landing page also included instructions on how to initiate the brief (about 5 minutes) secure screening assessment.

The study eligibility criteria assessed in the secure screening assessment were:

- Able to read and speak English
- Age 18 or older
- Currently living in the U.S.
- Regular use of a smartphone, the internet, or both
- Regular use of text messaging, email, or both
- Identify as having a Hereditary Cancer Syndrome (HCS)
- Have never been diagnosed with cancer
- Have a "low" level of resilience as indicated by a score of 26 or below on the Connor Davidson Resilience Scale (CD-RISC 10)

The screener excluded individuals who did not meet the study eligibility criteria. Individuals who screened out or who did not consent to study participation were thanked for their time and provided with a list of national resources for previvors.

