Eligible participants were invited to provide informed consent. Those who provided informed consent completed a baseline research assessment that assessed confidence to cope, psychological flexibility, depression, and anxiety. After completing the baseline assessment, participants completed their first session, which asked them a series of questions to determine their level of resilience. Based on responses during this first session, the system delivered tailored feedback and queued 30 days worth of daily, tailored text messages focused on resilience. Completing this first session marked the end of the baseline session (baseline research assessment + first session) and granted participants access to their online portal, which featured interactive activities and tools designed to address their resilience and coping. Participants were told they could access their online portal at any time during the 30-day pilot period. As a thank you for completing the baseline assessment, participants received a \$50 gift card.

Four days after completing the first session (which followed the baseline assessment), participants were prompted to complete a brief second session via text message. This session asked participants a series of questions related to an adaptive coping strategy: acceptance. Based on responses during that session, the system delivered tailored feedback and queued daily, tailored text messages about acceptance.

This pattern continued for the remainder of the 30-day pilot period: every four days, participants were prompted to complete a new session via text message, during which they would be asked a series of questions related to either resilience or an adaptive coping strategy; based on their responses, the system delivered tailored feedback and queued daily, tailored text messages related to the construct assessed.

Over the course of the 30-day pilot period, participants could complete up to seven sessions via SMS. The constructs assessed during each session were as follows: 1) resilience; 2) adaptive coping strategy: acceptance; 3) resilience; 4) adaptive coping strategy: active coping; 5) resilience; 6) adaptive coping strategy: venting; 7) resilience.

All daily text messages provided tailored guidance matched to each participant's responses to questions about their resilience and use of adaptive coping strategies, and encouraged users to engage with online portal activities and tools.

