Participants received an email 31 days after completing the baseline session (baseline research assessment + first session), participants received an email inviting them to complete the follow-up assessment. Up to four text and five email reminders to complete the follow-up assessment were sent. Non-respondents received up to two telephone calls from the Research Manager to remind them to complete the follow-up assessment and offer them the opportunity to complete the assessment by phone. As a thank you for completing the follow-up assessment, participants received a \$70 gift card.

Pilot participants were 138 previvors. Of the 138 initial participants, 134 completed the follow-up assessment at the end of the 30-day pilot period, resulting in a final sample of 134 previvors.

Simple descriptive statistics were calculated to describe the study sample and to evaluate program utilization and acceptability. Paired t-tests of pre-post differences on several key outcomes, including the primary outcome (resilience as measured by the CD-RISC 10), were conducted.

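### The SAP reads change on the CD-RISC 10 as the PreCharge effect in a group selected for low CD-RISC 10 scores, without naming the pretest administration, so regression to the mean may be counted as effect

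*SAP*

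**What the plan says.** The protocol's eligibility list (Methods) admits only people with low "resilience as indicated by a score of 26 or below on the Connor Davidson Resilience Scale (CD-RISC 10", assessed in the screener. The Design section describes one group measured before and after the program.

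The SAP states: "The primary outcome was change, from pretest (baseline) to posttest (30 day follow-up), in resilience", measured by the CD-RISC 10. On the analysis it states: "Paired t-tests were used to determine the effect of the *PreCharge* intervention on the primary and secondary outcomes". Cohen's d gives the size; its standardiser is not stated.

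On what was measured before the program, the protocol's Methods say that consenting participants "completed a baseline research assessment that assessed confidence to cope, psychological flexibility, depression, and anxiety". Resilience is not in that list, though the list is not said to be complete. Then "participants completed their first session, which asked them a series of questions to determine their level of resilience"; the instrument is not named. The same section adds: "Completing this first session marked the end of the baseline session (baseline research assessment + first session". The follow-up clock starts there too: "Participants received an email 31 days after completing the baseline session (baseline research assessment + first session".

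The protocol gives 138 enrolled and 134 analysed. The text available mentions neither regression to the mean nor a reference value for change other than zero.

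**The concern.** A paired t-test takes zero mean change as its null (this is implied by the test, not written in the SAP). People chosen because one reading on a scale was low will, on average, score higher when that scale is repeated, even if nothing has been done for them. When the entry score also serves as the pretest, zero is therefore not the expected change under no effect.

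The bias depends on which score is the pretest, and the documents do not say. The screener is the only CD-RISC 10 named before the program starts. Yet the protocol defines its baseline session without the screener, counts follow-up from that session, and says in the Design section: "Following the baseline assessment, participants received onscreen feedback tailored to their responses". This wording points to a score taken after eligibility was fixed.

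At stake is how the primary p-value and Cohen's d are read. As the SAP is worded, any part of the rise that comes from selecting low scorers is credited to the program. The direct selection problem concerns the CD-RISC 10. Secondary outcomes would be touched only through their correlation with the screening score.

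**Working it through.** The plan has no figure to reproduce: it gives no sample-size calculation, SD, alpha or target effect.

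**Inputs from the documents:** cut-off 26; n = 134 analysed.

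**Assumptions:** CD-RISC 10 scores normal among those screened, mean 28, SD 6; two-sided 0.05; no true effect; truncation at 26.5 because scores are whole numbers.

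**Step 1. How far the enrolled group lies below the screened group.**
- a = (26.5 − 28)/6 = −0.25; φ(a)/Φ(a) = 0.3867/0.4013 = 0.9636.
- D = 6 × 0.9636 = 5.78, so the enrolled mean is 28 − 5.78 = 22.22.
- Enrolled variance = 36 × (1 + 0.25 × 0.9636 − 0.9636²) = 11.25, SD 3.35.

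**Step 2. Screening score as pretest, retest correlation r.**
- Expected change = (1 − r) × D. At r = 0.8: 0.2 × 5.78 = 1.16 points.
- Variance of change = (1 − r)² × 11.25 + 36 × (1 − r²) = 0.45 + 12.96 = 13.41, SD 3.66.
- d on the SD of change = 1.156/3.66 = 0.32 (on the enrolled pretest SD, 1.156/3.35 = 0.35).
- The noncentral t with 133 degrees of freedom gives a 95% chance of p < 0.05.
- Truncating at 26 instead gives 1.23 points and 97%.
- Over screened means 22 to 32, SDs 5 to 7 and r from 0.6 to 0.95, the shift runs from 0.08 to 3.80 points, d (SD of change) from 0.05 to 0.78 and the false-positive rate from 9% to 100%.

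**Step 3. Pretest re-measured after eligibility.** Let r1 and r2 be the screener's correlations with pretest and posttest, and rpp the pre-post correlation.
- Expected change = (r1 − r2) × D.
- Variance of change = (r1 − r2)² × 11.25 + 36 × [(1 − r1²) + (1 − r2²) − 2(rpp − r1·r2)].
- Worked case, r1 0.90, r2 0.80, rpp 0.80: change = 0.10 × 5.78 = 0.58; variance = 0.11 + 36 × (0.19 + 0.36 − 0.16) = 14.15, SD 3.76; d = 0.154; false positives 42%.

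| r1 | r2 | rpp | Shift (points) | False positives |
|---|---|---|---|---|
| 0.80 | 0.80 | 0.80 | 0 | 5% |
| 0.85 | 0.80 | 0.80 | 0.29 | 14% |
| 0.90 | 0.80 | 0.70 | 0.58 | 30% |
| 0.90 | 0.80 | 0.80 | 0.58 | 42% |
| 0.90 | 0.80 | 0.90 | 0.58 | 71% |
| 0.95 | 0.80 | 0.80 | 0.87 | 76% |
| 0.90 | 0.70 | 0.70 | 1.16 | 83% |

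The documents give no interval between screening and baseline. If it was short, r1 may exceed the 30-day r2; nothing in the text shows that it did.

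**The case against.** The strongest reply is that the bias is conditional. On the reading that the text favours, the pretest comes after eligibility, and re-measuring is itself a partial or full protection: with r1 = r2 there is no bias and the error rate is 5%. This stands. What the documents show is an unnamed pretest and an unsupported effect claim, not a demonstrated bias.

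A second reply is that the percentages rest on assumed inputs and span nearly the whole scale, and that the 95% figure belongs to the less favoured reading. This also stands, so the figures are illustrations only.

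A third reply is that this is an openly single-group pilot whose stated purpose is acceptability and feasibility, and no decision rule is tied to the p-value in the text available. This lowers the stakes. It does not repair the SAP's sentence, which names a resilience outcome, tests it and calls the result the intervention's effect.

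A reader might go further and infer that the screener must be the pretest, because resilience is missing from the baseline list. The documents do not support this: the list is not stated to be exhaustive, the first session did ask about resilience, and the protocol's baseline session leaves the screener out. Part of the SAP was also not available to this review, so the statement that the pretest is unnamed covers only the text at hand.

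**Conclusion.** The point holds in conditional form. Selection was on the primary outcome scale, the test is uncontrolled, the pretest administration is not named, and the SAP attributes the change to PreCharge. Followed as written, the plan can count regression to the mean as a program effect.

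With a screening pretest the direction is certain (upward for any retest correlation below 1), and only the size is unknown. With a re-measured pretest, the bias is zero if the screener correlates equally with pretest and posttest, and positive if it correlates more strongly with the pretest.

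Two stronger conclusions are tempting. One is that the observed rise is an artefact. The other is that re-measurement settles the matter. Neither follows, because the documents give no screened mean, SD or correlation. It should be fixed, because the correction is cheap and touches the main statistical claim.

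**What to change.** 1. State which CD-RISC 10 administration is the pretest. Use a post-eligibility score if one exists. The protocol reports the tests as already done, so label the analysis post hoc if this changes it.
2. Reword the SAP's aim for the paired tests as estimating within-person change. Do not attribute that change to PreCharge, and add one sentence saying that selecting low scorers can produce a rise with no effect at all.
3. If the screening score is the pretest, also show the expected shift (1 − b) × D for b = 0.6, 0.7, 0.8 and 0.9 beside the observed change. Here D is the mean screening score of all otherwise-eligible people screened minus that of those analysed. In the illustrative case the rows are 2.31, 1.73, 1.16 and 0.58 points.
4. For a re-measured pretest, a short table of k × D for k = r1 − r2 from 0 to 0.20 is optional (0 to 1.16 points in the illustrative case).

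Set no pass/fail rule on any row, because this design cannot identify b or k. People who screened out did not reach consent, so their scores may not be usable; in that case show D over a stated range of screened means.

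Cost: one sentence naming the pretest, one rewording, one caveat and at most a short table, with no new data collection. The downside is a less favourable headline for resilience.

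### Does the plan need a named adaptive-coping outcome, given that coping is one of the programme's two targets?

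*SAP*

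**What the plan says.** The Objective in the Protocol describes a programme "designed to increase resilience and adaptive coping among previvors", while giving acceptability and feasibility as the purpose of the 30-day pilot.

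The SAP has one inferential method, the paired t-test between baseline and 30-day follow-up, with Cohen's d for magnitude. On outcomes it says "The primary outcome was change, from pretest (baseline) to posttest (30 day follow-up), in resilience as measured by the Connor Davidson Resilience Scale (CDRISC-10", and then "Secondary outcome measures include change in psychological flexibility", with the AAQ-II as instrument. The Protocol, at the end of Methods, speaks more broadly: "Paired t-tests of pre-post differences on several key outcomes, including the primary outcome".

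Coping appears in two places in Methods. At baseline, participants "completed a baseline research assessment that assessed confidence to cope, psychological flexibility, depression, and anxiety". During the pilot, up to seven sessions were offered by text message. In the first, at baseline, participants "completed their first session, which asked them a series of questions to determine their level of resilience". The rest covered "2) adaptive coping strategy: acceptance; 3) resilience; 4) adaptive coping strategy: active coping; 5) resilience; 6) adaptive coping strategy: venting; 7) resilience".

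**The concern.** A programme with two targets would normally have at least one outcome for each. Here resilience has the primary outcome, and coping has none by name.

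The obvious substitute, the session questions on coping, does not work. Acceptance, active coping and venting are each asked about in one session only. All three sessions come after the tailored messages had begun, so no change from before to after can be formed for any of them.

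If nothing else measured coping, the pilot would give no estimate for one of its two targets. A gain on CD-RISC 10 or AAQ-II might then be taken as evidence that the coping content worked, and that reading could pass into the design of a later trial.

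**Working it through.** The plan states no figure on this point, so there is none to reproduce. The check is a count of measurements, followed by a comparison of the passages.

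**1. Session counts (Protocol, Methods).**

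- The second session is timed thus: "Four days after completing the first session (which followed the baseline assessment), participants were prompted to complete a brief second session". Later sessions follow every four days.
- If each is completed when prompted, session k falls on day 4 × (k − 1), that is, days 0, 4, 8, 12, 16, 20 and 24.
- Resilience: sessions 1, 3, 5 and 7 (days 0, 8, 16 and 24), four values.
- Acceptance: session 2 (day 4), one value.
- Active coping: session 4 (day 12), one value.
- Venting: session 6 (day 20), one value.
- Share of sessions on coping: 3/7 = 42.9%.

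A paired difference needs two values per person on the same measure. Each coping strategy has one, so the session data give no paired test on coping. This part of the concern is correct.

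**2. What the session questions are for.** Methods describes them as input to the tailored feedback and to the queue of daily messages. Neither the analysis paragraph of Methods nor the SAP offers them as outcome data. The SAP takes change from the baseline and 30-day assessments. The count in step 1 therefore shows that these questions could not serve a use the plan never gave them.

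**3. What else could carry a coping outcome.**

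| Baseline research measure (Methods) | Named in the SAP as a pre-post outcome? |
|---|---|
| Confidence to cope | No |
| Psychological flexibility | Yes (AAQ-II) |
| Depression | No |
| Anxiety | No |

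Confidence to cope stands first in a list that also holds a named pre-post outcome. If it was asked again at follow-up, it gives one paired contrast on coping. The documents do not list the content of the follow-up assessment, so this can be neither confirmed nor excluded.

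**4. Whether the outcome list is closed.** The SAP introduces secondary outcomes with the verb *include* and then names one. The Protocol reports tests on *several* outcomes, while the SAP names two in all. Both wordings leave room for more. Part of the SAP file was also not available for this review, and nothing can be inferred from its absence. A name missing from the available text is thus weak evidence that an analysis is missing.

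**5. Effect on the named analyses.** The paired tests and Cohen's d for CD-RISC 10 and AAQ-II use only those two scales. They come out the same whether or not a coping measure is added.

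**The case for a change.** The strongest case for a change is that an open list is itself the fault. A reader cannot tell which tests belong to the plan, and the SAP says that it sets out to determine the programme's effect. Confidence to cope is also not the same thing as using acceptance, active coping or venting, so even a repeated measure of confidence would leave use of those strategies without a described before-and-after measurement. The AAQ-II has acceptance in its title, but the SAP assigns it to psychological flexibility, and it would not cover active coping or venting in any case.

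Much of this stands. The available text names no coping outcome, does not itemise the follow-up assessment, and describes no repeated measurement of strategy use.

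It does not follow that the plan produces a wrong or misleading result. The harm depends on someone crediting a resilience or flexibility gain to the coping content, and neither document makes that claim. In an uncontrolled pilot whose purpose is acceptability and feasibility, an effect estimate for every programme target is desirable but not required.

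**Conclusion.** No change to the plan. The session counts are right, but they concern data used for tailoring. The remaining gap is one of description: the status of confidence to cope as an outcome is not stated. Analysts who hold the follow-up data can settle it when they report, either by showing the paired change in confidence to cope with its interval if it was measured again, or by confining effect statements to resilience and psychological flexibility if it was not.

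In size, this is one measure of unstated status, with no effect on the CD-RISC 10 or AAQ-II results. The available text does not show whether an analysis of confidence to cope was planned in advance, so it should not be presumed post hoc.

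The conclusion rests on two readings: that the outcome lists are open, as their wording indicates, and that the session questions were meant only for tailoring, as Methods describes them. It would be different if a report claimed an effect on coping with no coping measure behind it.

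### Does naming Cohen's d without its standard deviation or a confidence interval call for a change to the SAP?

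*SAP*

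**What the plan says.** The SAP's single analysis paragraph sets the design ("This study involved a single-group, pre-post design"), the endpoint ("The primary outcome was change, from pretest (baseline) to posttest (30 day follow-up), in resilience") and the test ("Paired t-tests were used to determine the effect of the" intervention on primary and secondary outcomes). Effect size gets one closing sentence: Cohen's "d was used to assess the magnitude of the differences". There is no formula, and no interval for d or for the mean change.

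The Protocol's Methods section adds only descriptive statistics and "Paired t-tests of pre-post differences on several key outcomes, including the primary outcome". Three other facts there bear on the point:

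- Entry required a low "level of resilience as indicated by a score of 26 or below on the Connor Davidson Resilience Scale (CD-RISC 10"), which is the primary outcome scale.
- After consent, participants completed a "baseline research assessment that assessed confidence to cope, psychological flexibility, depression, and anxiety". The CD-RISC 10 is not in that list, although resilience was scored at screening and asked about again in the first session.
- 138 people entered and 134 completed follow-up.

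**The concern.** In a paired design, Cohen's d has several common forms: mean change divided by the pretest SD, by the pooled pretest and posttest SD, or by the SD of the change scores (d_z). These are different quantities, and a reader given only the label cannot tell which one was computed.

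Selection seems to sharpen the problem. If the screening score is the pretest, the cut at 26 removes the upper part of its distribution and shrinks its SD. The follow-up SD partly recovers, so the denominators separate. Because d is the only standardised magnitude the SAP names, an unlabelled value could be compared wrongly with values from unselected samples. It could also be carried into a later sample-size calculation. Sample size scales with 1/d², so a 1.13 to 1.69-fold spread in d would become about 1.3 to 2.8-fold in n (1.13² = 1.28; 1.69² = 2.86, or 2.8 before rounding).

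**Working it through.** **Inputs.** From the documents: entry at 26 or below, a paired t-test, 134 pairs. The documents state no d, SD, correlation or expected change, so there is no figure to reproduce. Assumed for illustration: unselected scores normal with mean 28 and SD s = 6; pre-post correlation before selection ρ = 0.6 to 0.9; pretest equal to the screening score; cut at 26.5 for an integer score; mean change 3 points.

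**Pretest SD after selection.** z = (26.5 − 28)/6 = −0.25; λ = φ(z)/Φ(z) = 0.3867/0.4013 = 0.9636. V_pre = s²(1 − zλ − λ²) = 36 × (1 + 0.2409 − 0.9284) = 11.25, so the SD is 3.35.

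**Other SDs, shown at ρ = 0.8.**

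- V_post = ρ²V_pre + s²(1 − ρ²) = 7.20 + 12.96 = 20.16; SD 4.49.
- V_change = (1 − ρ)²V_pre + s²(1 − ρ²) = 0.45 + 12.96 = 13.41; SD 3.66.
- Pooled SD = √((11.25 + 20.16)/2) = 3.96.

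Dividing 3 by each SD gives the d values below.

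**The comparison that decides the selection argument.** Without selection the pretest and posttest SDs are equal. The pretest and pooled versions then coincide, and d_z divided by either is 1/√(2(1 − ρ)).

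| ρ | d, pretest SD | d, pooled SD | d_z | Largest/smallest, selected | Largest/smallest, unselected |
|---|---|---|---|---|---|
| 0.6 | 0.89 | 0.69 | 0.60 | 1.49 | 1.12 |
| 0.7 | 0.89 | 0.72 | 0.68 | 1.31 | 1.29 |
| 0.8 | 0.89 | 0.76 | 0.82 | 1.18 | 1.58 |
| 0.9 | 0.89 | 0.81 | 1.14 | 1.40 | 2.24 |

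Selection widens the spread at 0.6, leaves it about the same at 0.7, and narrows it at 0.8 and 0.9. I repeated this for unselected means of 24, 26, 28 and 30 and SDs of 5, 6 and 7. At 0.8 and 0.9 selection narrows the spread in every case. At 0.7 it narrows it for means 24 and 26 and widens it for 28 and 30. At 0.6 it widens it throughout. Across these cases the selected spread runs from 1.13 to 1.69.

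**Against sampling error.** The 95% half-width of d_z at n = 134 is 1.96 × √(1/n + d²/(2n)), which is 0.18, 0.20 and 0.22 at ρ = 0.6, 0.8 and 0.9. At ρ = 0.8 the versions span about 0.14, inside that half-width. At 0.6 they span 0.29 and at 0.9 about 0.32, both outside it.

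**What the test sees.** The paired t statistic is mean change divided by (SD of change/√n). At ρ = 0.8 that is 3/(3.66/√134), about 9.5, whichever d is printed. A reported t gives d_z = t/√134 and, through the noncentral t distribution, its interval; for example d_z = 0.5 gives 0.32 to 0.68. Mean change divided by t gives its standard error, and hence its interval. Only the pretest-SD and pooled-SD versions need further SDs.

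**The case for a change.** The best case for a change is that magnitude is a main product of a single-group pilot, that d is the only standardised measure named, and that the remedy is cheap: a formula, an interval and three SDs per outcome. Much of this stands. The omission is plain, and a published d should carry its formula. Selection does have one consistent effect: it raises d on the pretest SD relative to an unselected sample, by 6/3.35 = 1.79 in the example and 1.43 to 2.05 over the assumed range. The pooled-SD version rises 1.24 to 1.80 times, while d_z moves by only 1% to 9%. A d on the pretest SD from this trial should therefore not be set beside values from unselected groups without comment. This applies to the primary outcome only, since entry was not restricted on the psychological flexibility scale. It is strongest if the screening score is the pretest. If the scale was given again, correlating 0.8 to 0.9 with screening, d on the pretest SD drops from 0.89 to between 0.67 and 0.75.

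The sample-size argument does not stand. Each design formula takes its own d: d_z for a paired comparison, a between-person SD for a comparison of post scores. The 1.3 to 2.8-fold discrepancy arises only if someone enters the wrong one, and the documents describe no such use. The Protocol's stated purpose is acceptability and feasibility.

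Two neighbouring questions are separate: which resilience score serves as the pretest, and regression to the mean in a group selected for low scores. No choice of denominator settles either.

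**Conclusion.** The concern describes a true gap in detail, but not one that requires a change to the plan. The test, the endpoint and the estimate of mean change are all specified without reference to d. No threshold, benchmark or go/no-go rule depends on it, and an analyst following the SAP reaches the same paired-test conclusion under any definition. Supplying the formula, the mean change with its interval, and the pretest, posttest and change SDs is ordinary good reporting from data already in hand. It involves no choice of a better analysis.

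The versions of d would differ by a factor of 1.13 to 1.69 on assumed inputs: a normal unselected distribution with mean 24 to 30 and SD 5 to 7, correlation 0.6 to 0.9, and the screening score as pretest. None of these comes from the documents. The ambiguity belongs to paired designs generally, and the entry cut at 26 widens or narrows it depending on the correlation. Readers should look for the label on any reported d and be cautious in comparing a pretest-SD or pooled-SD value for resilience with unselected samples.
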